This will be a single-center, double-blinded, parallel-group, randomized, placebo-controlled trial. Older adults with sarcopenic obesity (n= 105) will be allocated to one of three groups: protein supplementation (PTN, n=35), placebo supplementation (PLA, n=35), or control (CON, n=35). The PTN and PLA groups will receive dietary supplements in addition to an exercise training and calorie restriction intervention, while the CON group will receive no intervention. Body composition, bone health, cardiorespiratory fitness, pulmonary function, functional capacity, muscle cross-sectional area, upper and lower-limb maximal dynamic strength, endothelial function, biochemical parameters, health-related quality of life, cognitive function, sleep quality, symptoms of anxiety and depression, and nutritional status will be assessed before and after a 16-week intervention period. A linear mixed model with repeated measures analysis will be conducted to assess within- and between-group effects of the intervention, using baseline values of the outcome as covariates. Whenever significant group-by-time interactions will be found, post-hoc tests on the adjusted predictions with Sidak's adjustment will be performed for multiple comparisons. Significance will be set at $p<0.05$. Data will be reported as the mean and standard deviation, along with the estimated mean difference (EMD) between groups and its 95% confidence interval (95% CI) when a main effect or interaction is observed.

BACKGROUND AND SIGNIFICANCE

The prevalence of obesity among older adults is growing worldwide (1-3). Excessive adipose tissue is linked to insulin resistance, high blood pressure, endothelial dysfunction, and dyslipidemia, obesity offers a heightened risk for developing cardiovascular and metabolic diseases, particularly among older individuals (4-6). Concurrently, aging is associated with declines in skeletal muscle mass and function (i.e., sarcopenia) (7), which can be further exacerbated by obesity (8-10). The interplay of these conditions poses an emergent public health issue termed sarcopenic obesity (11-13), a condition associated with greater risk of morbimortality and worse health-related quality of life (14, 15).

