The present study will be a single-center, double-blinded, parallel-group, randomized, placebo-controlled trial. Figure 1 illustrates the study design. Initially, participants will be pre-screened through phone calls or personal interviews. Those who meet the preliminary criteria will then be further assessed for their medical condition and eligibility criteria. Eligible participants will be matched based on sex and then randomly allocated in a 1:1:1 ratio into one of the following experimental groups: (a) protein supplementation (PTN), (b) placebo supplementation (PLA), or (c) control (CON). Both the PTN and PLA groups will receive dietary supplementation, will be caloric-restricted, and will engage in an exercise training program. Participants in the CON group will receive no intervention other than general guidance on healthy eating and physical activity. All outcomes of interest will be assessed immediately before participants' randomization at baseline (PRE) and after 16 weeks of intervention (POST). Anthropometric and dietary parameters will be reassessed at weeks 4, 8, and 12. Participants will also meet with a registered dietitian from the research team every two weeks in order to ensure compliance with the dietary intervention.

RANDOMIZATION

Eligible participants will be sex-matched and then randomly allocated using a computer-generated block design in a 1:1:1 ratio into one of the following experimental groups through a specific software (<https://randomizer.org>): (a) protein supplementation (PTN), (b) placebo supplementation (PLA), or (c) control (CON). The allocation sequence will be concealed from the research staff.

EXAMINATIONS

The primary outcome will be the change from baseline in fat-free mass (total, appendicular, appendicular relative to BMI and leg). Secondary outcomes will include other measures of body composition (i.e. fat and bone density), bone microarchitecture, bone metabolism, and specific muscle functions. Other outcomes, including cardiopulmonary capacity (cardiorespiratory fitness and pulmonary function), glycemic control, insulin sensitivity, endothelial function, inflammation, cognitive function and

related cellular and molecular mechanisms (telomere length, oxidative stress, and lipid profile) will also be assessed.

Anthropometry

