Sample size was determined a priori using the G-Power software (Version 3.1.9.2, University of Kiel, Germany). The analysis was conducted by inputting α error (0.05), power ($1 - \beta$ error = 0.95), and effect size (Hedges' g = 0.61), considering previous data indicating a lower loss of fat-free mass in individuals undergoing caloric restriction who had an increase in protein intake compared to their counterparts who maintained their usual protein intake (31). Calculations were based on an ANOVA with repeated measures (within-between interactions) and the total sample size was determined to be 81 individuals. To account for midtrial withdrawals, the sample will be increased by ~30% (i.e. 105 participants).

DATA ANALYSIS

Data will be presented as mean \pm standard deviation (SD), estimated mean difference between groups (EMD) at POST (only in the presence of group x time interaction), 95% confidence interval (95%CI), unless otherwise indicated. Baseline characteristics will be compared between groups using either Fisher exact test or generalized linear model with Sidak post hoc adjustment whenever necessary. Data will be analyzed using an intention-to-treat (ITT) approach to preserve the integrity of randomization. Before inferential analysis, outliers will be identified, and the data will be tested for homogeneity of variance and sphericity. Dependent variables will be analyzed by a linear mixed model analysis for repeated measures (assuming time [PRE and POST] and group [PTN, and PLA] with baseline values as covariate. The restricted maximum likelihood method, compound symmetry covariance structure, and Kenward-Roger degrees of freedom approximation will be applied for all models. In order to maintain the overall significance level at 0.05, the primary endpoints will be assessed using Hochberg's procedure (124). For all secondary outcomes the significance level will be set at $p \leq 0.05$. Whenever significant group-by-time interactions are identified, post-hoc tests on the adjusted predictions with Sidak's adjustment will be performed for multiple comparisons.

All analyses will be performed in the statistical environment R (version 3.5.3; R Core Team 2020).

STATISTICAL ANALYSIS PLAN

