All analyses will be performed in the statistical environment R (version 3.5.3; R Core Team 2020). We will perform all the comparisons using two-sided significance tests. Intention-to-treat analyses will be performed by analyzing data from all participants originally randomized to preserve the integrity of randomization. The longitudinal analysis of all outcomes will be performed using a linear mixed model for repeated measures, assuming 'group' (PTN, and PLA) and 'time' (pre-intervention and post-intervention) as fixed factors, and 'subjects' as a random factor, with an interaction between 'group' and 'time' added to the model; baseline values of the outcome will be used as covariates. For all models, maximum restricted likelihood and Kenward-Roger degrees of freedom will be used for model fit and estimation. We will adjust for testing of the four primary outcomes, total fat-free mass, appendicular fat-free mass, appendicular fat-free mass relative to body mass index, and leg fat-free mass, using Hochberg's procedure in order to maintain the overall significance level at 0.05. Since the other hypothesis tests (for the secondary outcomes) will be more exploratory in nature, the Hochberg's correction will not be used, and two-sided p-values less than 0.05 will be considered to indicate statistical significance. For both primary and secondary outcomes, whenever significant group-by-time interactions are identified, post-hoc tests on the adjusted predictions with Sidak's adjustment will be performed for multiple comparisons.

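### The plan shows the PTN minus PLA difference only when a test triggers it; its two stated triggers conflict, and the four primary outcomes are not exempt

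*Combined protocol and SAP*

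**What the plan says.** Three places bear on this.

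- **Data Analysis** lists what will be presented. It includes the "estimated mean difference between groups (EMD) at POST (only in the presence of group x time interaction"; the 95% CI follows as a separate list item, and a closing rider allows for exceptions indicated elsewhere.
- **Summary of Study** says data will be given as mean and SD, "along with the estimated mean difference (EMD) between groups and its 95% confidence interval (95% CI) when a main effect or interaction is observed".
- **Statistical Analysis Plan** section: "For both primary and secondary outcomes, whenever significant group-by-time interactions are identified, post-hoc tests on the adjusted predictions with Sidak's adjustment will be performed".

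The groups in the model are two, "assuming 'group' (PTN, and PLA) and 'time' (pre-intervention and post-intervention) as fixed factors", so the between-group difference is PTN minus PLA. In the Examinations section, "The primary outcome will be the change from baseline in fat-free mass (total, appendicular, appendicular relative to BMI and leg". The SAP section makes these four measures subject to Hochberg's procedure: "We will adjust for testing of the four primary outcomes, total fat-free mass, appendicular fat-free mass". It sets no separate presentation rule for them.

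**The concern.** The stated aim is the added effect of protein on fat-free mass in people who all train and restrict calories. PTN minus PLA is that effect. Under either wording, its presentation depends on a test result.

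The two wordings can also disagree on the same data. Both arms receive exercise and caloric restriction, so a clear time effect without an interaction is plausible. One reading of the Summary would then release the difference, while Data Analysis would withhold it. An analyst could choose between them after seeing the results and still be following the protocol.

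Two things are at stake. A primary outcome without a detected interaction may be reported without the estimate and interval that show whether a worthwhile effect is ruled out or merely undetected. And the differences that do appear are a selected set, which tends to exaggerate when power is modest.

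**Working it through.** **1. The text.**

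| Place | Trigger | What is conditional | Primaries exempt? |
|---|---|---|---|
| Data Analysis | group x time interaction | difference at POST; CI unclear | no |
| Summary of Study | main effect or interaction | difference and CI | no |
| SAP section | significant interaction | post-hoc contrasts | no, primaries named |

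No section uses the Data Analysis rider to exempt the primaries. No section says whether the trigger for a primary is unadjusted p<0.05 or significance under Hochberg, whose strictest step is 0.05/4 = 0.0125.

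**2. Inputs from the documents.** Sample Size Calculation: Hedges' g = 0.61, power 0.95, N = 81, raised to 105. Per arm: 81/3 = 27 and 105/3 = 35. The inflation reproduces (81 x 1.3 = 105.3). The 81 cannot be uniquely reproduced, because the correlation, the number of groups and the conversion of g to f are not stated. With f = 0.61/2 = 0.305 and three groups, N is 87 at correlation 0, 81 at 0.07 and 45 at 0.5. Nothing below depends on this.

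**3. Assumptions, not in the documents.** PRE-POST correlation r of 0.8 to 0.95, true effects of 0, 0.3 and 0.61, equal PRE and POST variance, no dropout. The unit of 0.61 is not stated, so both readings are shown. An effect d in POST-SD units equals d/sqrt(2(1-r)) in SD-of-change units; at r = 0.8, 0.61/sqrt(0.4) = 0.96.

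**4. How often the difference is withheld (SD-of-change units, interaction-only rule).** The estimate must exceed t x sqrt(2/n):

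- n = 35, p<0.05: 1.995 x 0.239 = 0.48
- n = 27, p<0.05: 2.007 x 0.272 = 0.55
- n = 35, p<0.0125: 2.566 x 0.239 = 0.61

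For a true 0.61, with 35 [27] per arm:

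- At 0.05: withheld in 29% [41%]; averages 1.19 [1.29] times the truth when shown.
- At 0.0125: withheld in 50% [63%]. This is the upper end for a primary, since Hochberg's other steps are less strict.

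A true 0.3 at 0.05 is shown in 24% [19%], at 2.0 [2.2] times the truth.

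In POST-SD units at r = 0.8, a true 0.61 is shown in 98% [94%] at 1.01 [1.04] times, and a true 0.3 in 50% [40%] at 1.40 [1.54] times.

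**5. Would the withheld interval still contain 0.61?** At n = 35 a non-significant estimate between 0.61 - 0.48 = 0.13 and 0.48 leaves it inside. Share of untriggered results (p<0.05), 35 [27] per arm:

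| True effect | SD-of-change units | POST-SD units, r = 0.8 |
|---|---|---|
| 0 | 28% [40%] | 0.6% [4%] |
| 0.3 | 68% [75%] | 9% [31%] |
| 0.61 | 91% [94%] | 27% [64%] |

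At r of 0.9 or more, the POST-SD shares are about 1% or less.

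**6. What a reader could rebuild (35 per arm, POST-SD units).** From POST means and SDs the CI half-width is 1.995 x sqrt(2/35) = 0.48, against 0.29/0.21/0.15 for the baseline-adjusted estimate at r = 0.8/0.9/0.95. From change means and SDs it is 0.30/0.21/0.15, so almost nothing is lost. The plan does not say which will be tabulated.

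**7. If a time main effect also triggers.** For a true 0.3 SD of change at 35 per arm, the difference is shown in 27%, 76% or 99% of trials, at 1.83, 1.09 or 1.00 times the truth, when the mean change is 0, 0.3 or 0.5 SD.

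**8. Which contrast to report.** The model keeps PRE as a response, and "baseline values of the outcome will be used as covariates". At r = 0.8 the residual variances are then 0.01 at PRE and 0.37 at POST, but the model assumes a common value of about 0.19. The POST standard error is about sqrt(0.19/0.37) = 0.72 of its true size. Simulated coverage of the nominal 95% CI at POST is about 83-84%. The group x time contrast covers 94-95%, and a POST-only model adjusted for baseline covers 95%.

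**The case against.** The strongest reply is that nothing is lost in estimation. With two groups and two times, the group x time coefficient in the SAP section is the PTN minus PLA difference in change, and it is fitted for every outcome. The SAP section restricts post-hoc tests and contains no rule on presenting the difference. Data Analysis speaks of the presence of an interaction rather than its significance, lists the CI separately and allows exceptions. Group means and SDs appear in any case. Selection may also be negligible: if power is really 95%, or if a time effect releases the estimate and both arms change clearly, nearly every difference would be shown.

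Much of this stands, and it limits the point to presentation. It does not remove it. No section uses the exception for the primaries, the Summary plainly makes the CI conditional, and the two triggers remain different.

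A reader might infer more than the documents support:

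- **That the effect will not be estimated.** It will be; only its presentation is conditional.
- **That most unreported intervals would leave 0.61 open, or that almost none would.** Neither holds in general. The share runs from near zero to 94%, depending on the unit of 0.61, r, the true effect and the arm size.
- **That published differences will be materially exaggerated.** That needs modest power, which the documents neither establish nor exclude.

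**Conclusion.** The point holds as a defect in the presentation rules. The conflict between the Summary and Data Analysis, and the lack of any exemption for the four primaries, are matters of text and rest on no assumption. Whether a primary's trigger is unadjusted or Hochberg-adjusted is also unstated.

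The size is conditional. If 0.61 is in SD-of-change units, withholding a true effect of that size is common (29-41% at p<0.05, up to 50-63% at the strictest Hochberg step) and the exaggeration moderate. If it is in POST-SD units, the loss at 0.61 is small, though smaller true effects are still selected at r = 0.8. These figures assume the values of r and the true effects listed above, equal variances and no dropout.

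The poor coverage of the POST contrast is a related but separate defect. It would exist even if every difference were reported, and it matters here only for choosing which contrast to show. Overall, this should be changed: the repair is nearly free and concerns the trial's main estimate.

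**What to change.** - For all four primary outcomes, report the PTN minus PLA effect with 95% CI and p-value whatever the test shows. Preferably use the same table format for the secondary outcomes.
- Use Hochberg's procedure to decide what may be claimed, not what is displayed.
- Put one wording in the Summary of Study, Data Analysis and Statistical Analysis Plan sections.
- Name the source of the estimate: either the group x time contrast, which is the difference in change and matches the Examinations section, or a POST-only model adjusted for baseline. Do not use the POST contrast of the model as written.
- Report contrasts with the control group the same way only if that group is added to the model.

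The cost is a few sentences, a short specification of the contrast and extra table columns. No new data or participants are needed.

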glycemic control and insulin sensitivity, endothelial function, inflammation, and related cellular and molecular mechanisms (telomere length, oxidative stress, and lipid profile). We hypothesized that this integrated approach could provide substantial benefits for body composition, and various health-related outcomes crucial to managing sarcopenic obesity in this population.

STUDY HYPOTHESIS

We hypothesized that protein supplementation can provide additional benefits on body composition and bone health more than only caloric restriction and exercise training in this population. Additionally, we hypothesized that these improvements would enhance muscle function. Furthermore, we also expected that protein supplementation would enhance the effects of caloric restriction and exercise training on glycemic control, insulin sensitivity, endothelial function, inflammatory markers, lipid profile, telomere length and oxidative stress markers.

AIM

This study aimed at investigating the impact of protein supplementation in addition to exercise training and caloric restriction on fat-free mass (as primary outcome) in older adults with sarcopenic obesity. Secondary outcomes include skeletal muscle fiber area, muscle strength and functionality, fat mass (total, visceral and subcutaneous), bone health parameters (bone mineral density, microarchitecture and bone metabolism markers). In addition, this study will aim the effects of protein supplementation in other outcomes including cardiopulmonary capacity (cardiorespiratory fitness and pulmonary function), glycemic control and insulin sensitivity, endothelial function, inflammation, and related cellular and molecular mechanisms (telomere length, oxidative stress, and lipid profile).

RESEARCH DESIGN AND METHODS

This 16-week study will be a single-center, double-blinded, parallel-group, randomized, placebo-controlled trial.

STUDY POPULATION

Older adults will be recruited from the Division of Geriatrics at the School of Medicine of the University of São Paulo, as well as through advertisements on social media and in community-based centers for older adults. All participants will provide written informed consent before enrollment in the study.

Inclusion criteria

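### Non-primary outcomes are labelled exploratory, yet any with an unadjusted p below 0.05 would be called statistically significant, and only outcomes passing the interaction test get a between-group estimate

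*Combined protocol and SAP*

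**What the plan says.** - **Primary outcomes (Statistical Analysis Plan).** "We will adjust for testing of the four primary outcomes", using Hochberg's procedure. These are total, appendicular, BMI-relative appendicular and leg fat-free mass.
- **All other outcomes (same section).** One sentence gives both the label, "Since the other hypothesis tests (for the secondary outcomes) will be more exploratory in nature", and the rule, "the Hochberg's correction will not be used, and two-sided p-values less than 0.05 will be considered to indicate statistical significance".
- **Data Analysis section.** "For all secondary outcomes the significance level will be set at" p ≤ 0.05. The Statistical Analysis Plan uses p < 0.05; the difference is trivial.
- **Contrast and sidedness.** The model is fitted "assuming 'group' (PTN, and PLA) and 'time' (pre-intervention and post-intervention) as fixed factors", with their interaction. On sidedness: "We will perform all the comparisons using two-sided significance tests".
- **Sidak adjustment.** It applies within a single outcome, after that outcome's interaction is significant. It does not act across outcomes.
- **Display of estimates.** The Data Analysis section presents the estimated mean difference at POST only if there is a group-by-time interaction. The Summary of Study has a similar condition, a main effect or an interaction.
- **Hypotheses (Study Hypothesis).** The sponsor expects that "protein supplementation can provide additional benefits on body composition and bone health more than only caloric restriction and exercise training". It also expects gains in muscle function, glycemic control, insulin sensitivity, endothelial function, inflammation, lipids, telomere length and oxidative stress.

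**The concern.** Leaving exploratory outcomes unadjusted is acceptable. The difficulty is that the label and the rule do not match: the tests are called exploratory, but each receives a verdict of statistical significance at 5%, and benefit hypotheses are stated in advance for many of them. The Aim and Examinations sections separate secondary outcomes from other outcomes. The Statistical Analysis Plan knows only primary and secondary, and it ranks nothing within the non-primary set.

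The display rule makes this worse. Because the interaction test decides which outcomes get a between-group estimate, chance findings would appear with an estimate and interval, while the null results needed to judge them would not. Hochberg's control of the four primary outcomes does not protect conclusions drawn from that filtered list.

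**Working it through.** The documents give neither a number of non-primary outcomes nor an expected number of false positives, so there is no plan figure to reproduce. The count below is a reading of the Examinations section, with one analysed variable per named measure.

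**Step 1. Count.**

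| Domain | Variables |
|---|---|
| Anthropometry | 3 |
| Fat mass 1, aBMD 4, BMC 1 | 6 |
| Muscle cross-sectional area (CT 1, ultrasound 2) | 3 |
| Visceral and subcutaneous fat | 2 |
| Biopsy | 7 |
| HR-pQCT | 12 |
| Strength 3, function 3 | 6 |
| Pulmonary function | 6 |
| Cardiopulmonary exercise test | 9 |
| Lipids 6, glycated hemoglobin 1 | 7 |
| Oxidative stress | 6 |
| Gut hormones 4, inflammation 7 | 11 |
| Bone-related serum markers | 6 |
| OGTT | 6 |
| Telomere length | 1 |
| SF-36 (8 domains, 2 summaries) | 10 |
| Sleep 1, depression and anxiety 2 | 3 |
| Trail Making 2, Stroop 3 | 5 |
| Endothelial function (named as an outcome) | 1 |
| **Total** | **110** |

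A stricter rule drops the eight SF-36 domains, anthropometry and endothelial function: 110 − 8 − 3 − 1 = 98. A wider rule adds fiber types, percent-predicted values, subscores and diet, and reaches 144.

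The outcomes named as secondary in the Aim come to about 36: fat mass 1, visceral and subcutaneous fat 2, aBMD 4, BMC 1, HR-pQCT 12, bone serum markers 6, strength 3, function 3, fiber area 1, whole-muscle area 3. Whole-muscle area is a judgement call; without it the count is 33.

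**Step 2. Expected false positives if protein has no effect.** Assume one protein-versus-placebo interaction test per outcome, each with a true size of 5%. The expected number is the count × 0.05. This does not require independence.

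- 110 × 0.05 = 5.5
- 98 × 0.05 = 4.9
- 144 × 0.05 = 7.2
- Secondary tier only: 36 × 0.05 = 1.8

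**Step 3. Direction.** The tests are two-sided, so under no effect about half of the false positives favour protein: 110 × 0.025 = 2.75.

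**Step 4. Chance of at least one false positive, in either direction.** The correlations are assumptions; the documents give none.

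| Assumption | Chance of at least one |
|---|---|
| Independent, 1 − 0.95^110 | 99.6% |
| 12 independent blocks of 9; correlation 0.3, 0.5, 0.7 within a block (simulated) | 99%, 97.5%, 93% |
| One common correlation of 0.3 across all 110 (simulated) | about 95% |
| One common correlation of 0.5 across all 110 (simulated) | about 80% |

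The mean stays at 5.5 for 110 outcomes, but the spread widens with correlation. The 5th to 95th percentile of the number of false positives is 2 to 9 if independent, 1 to 17 (median 4) at a common correlation of 0.3, and 0 to 23 (median 2) at 0.5.

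**Step 5. Chance of at least one false benefit.** If independent, 1 − 0.975^110 = 94%. In the block simulation it is 0.89, 0.82 and 0.72 at correlations of 0.3, 0.5 and 0.7. The chance of two or more is 0.68, 0.61 and 0.53.

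**The case against.** The strongest reply is that this is ordinary, disclosed practice. The plan pre-specifies four primary endpoints with multiplicity control, labels the rest exploratory and says openly that no correction is used. Nowhere does it say that a secondary result will support an efficacy claim. That stands: the plan conceals nothing, and no family-wise adjustment of the exploratory tier is needed. What remains is the significance verdict attached to that tier, together with the display rule.

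The scope of the rule is also open to challenge. Both rule sentences name secondary outcomes, while the Aim and Examinations sections list a separate group of other outcomes. Applying the rule to all 110 is an inference. It is a reasonable one, since the Statistical Analysis Plan fits one model to every outcome and recognises no third tier, but the secondary-only figure of 1.8 belongs beside the 5.5.

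A reader might go further and infer that the rule almost guarantees a list of apparent benefits of protein. The documents do not support that. With two-sided testing the expected number of false benefits is 2.75, and under the block correlations the chance of two or more is 53% to 68%. Nor does the plan declare every outcome significant; each would be so declared only if its p-value fell below the threshold.

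**Conclusion.** The point holds as a mismatch between label and rule, aggravated by showing estimates only after a significant interaction. If protein has no effect, about 5.5 false positives are expected on average across about 110 variables (4.9 to 7.2 for 98 to 144), about 2.75 of them in the direction of benefit. The named secondary tier alone gives about 1.8. The chance of at least one in either direction is 99.6% under independence and about 80% to 99% under the assumed correlations.

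These figures rest on a count made from the Examinations section, one interaction test per outcome and a true 5% test size. Reporting on main effects as well, which the Summary of Study allows, would add tests. The 5.5 is an average, not a forecast for this trial. The primary analysis is unaffected, so this is an inexpensive improvement and not a threat to the main result.

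**What to change.** In the Data Analysis and Statistical Analysis Plan sections, replace the significance rule for non-primary outcomes with:

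> Secondary and other outcomes are all reported as PTN-PLA differences with 95% CIs and nominal, unadjusted p-values, whether or not the interaction is significant; none is called statistically significant and none supports an efficacy claim.

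Delete the Data Analysis condition that limits the estimated difference to outcomes with a group-by-time interaction, and bring the matching sentence in the Summary of Study into line.

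A false-discovery-rate rule applied within domains is a tempting alternative, but it is not recommended. The documents define no multiplicity domains, so the grouping would have to be invented. With 25 groups, for example, the chance of at least one false flag under no effect would still be 1 − 0.95^25 = 72% if independent, and single-variable groups would still be tested at an unadjusted 0.05.

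The cost is wording only, with no new data, visits or participants. Fewer secondary results can be labelled significant, and the results tables become longer.
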